1.1 Synopsis

Sponsor Name: Laboratorios Sophia, S.A. de C.V.	
Product Name: PRO-231	
Active ingredient name: Moxifloxacino hydrochloride	
Title of the study: Phase I clinical study, to evaluate the safety and tolerability of PRO-231 ophthalmic solution, versus VIGAMOXI,® on the ocular surface of ophthalmologically and clinically healthy subjects.	
Study Number: SOPH231-1 2 21/I	Date of creation: Dec 1st-21
Protocol version: 2.0	Release Date: 27-Jul-22
Therapeutic indication: Ocular antibiotic.	Use: Conjuntivitis bacteriana
Estimated duration of the study (from the first patient's first visit to the preparation of the final report): 5 to 6 months	Clinical Development Phase: I
Objectives: Main objective: 
• To evaluate the safety and tolerability of the PRO-231 formulation, versus VIGAMOXI,® on the ocular surface of ophthalmologically and clinically healthy subjects. Specific objectives: 
• Primary:	

- To assess the safety of PRO-231 ophthalmic solution applied to the ocular surface, in healthy volunteers, versus VIGAMOXI,® by:
 - To compare the incidence of adverse events (AEs), unexpected, related to interventions.
 - Incidence of conjunctival hyperemia and/or chemosis between interventions.
 - Changes in best-corrected visual acuity (MCVA) assessed with the Snellen chart between interventions.
 - Changes in ocular surface integrity using fluorescein staining, using the Oxford scale between interventions.
- To evaluate the tolerability of PRO-231 ophthalmic solution applied to the ocular surface, in healthy volunteers, versus VIGAMOXI,® by:
 - Changes in Eye Comfort Index (JI) score between interventions.
- *Side:*
 - To assess the safety of PRO-231 ophthalmic solution applied to the ocular surface, in healthy volunteers, versus VIGAMOXI,® by:
 - Incidence of expected and intervention-related AEs (excluding conjunctival hyperemia and/or chemosis).
 - To evaluate the tolerability of PRO-231 ophthalmic solution applied to the ocular surface, in healthy volunteers, versus VIGAMOXI,® by:
 - Presence of ocular symptoms (burning, foreign body sensation, pruritus and tearing) between interventions.

Hypothesis:

H_0 = PRO-231 ophthalmic solution has a safety and tolerability profile similar to that of VIGAMOXI® in clinically healthy subjects.

$$H_0: ST_A = ST_B \text{ o } ST_A - ST_B = 0$$

H_1 = PRO-231 ophthalmic solution does not have a similar safety and tolerability profile as VIGAMOXI® in clinically healthy subjects.

$$H_1: ST_A \neq ST_B \text{ o } ST_A - ST_B \neq 0$$

Operational definition of similarity: To reject H_0 , the p-value in the primary variables must be ≤ 0.05 and the 95% CI of this difference must not include zero. Both conditions for hypothesis testing (p-value and 95% CI) must be met, otherwise the result will be interpreted as "**absence of evidence**", not "**evidence of absence**".

Study Design: Phase I clinical study, controlled, comparative, parallel-group, single-blind, single-center.
Number of subjects (planned and analyzed): Number of planned subjects: 38 (19 subjects per arm).
Diagnosis and main inclusion criteria: Ophthalmologically and clinically healthy subjects.
Selection criteria: Inclusion criteria: 
– Have the ability to voluntarily give their signed informed consent.– Ophthalmologically and clinically healthy subjects.– Be able and willing to comply with scheduled visits, treatment plan, and other study procedures.– Age 18 to 45 years.– Both sexes.– Women of childbearing potential must ensure the continuation (initiated \geq 30 days prior to signing the informed consent form [ICF]) of the use of a hormonal contraceptive method or intrauterine device (IUD) during the study period.– AVMC of 20/30 or better in both eyes.– Corneal staining \leq grade I on the Oxford Scale.– Have an intraocular pressure \geq 10 and \leq 21 mmHg. Exclusion criteria: 
– History of hypersensitivity to fluoroquinolones or any of the components of the PI.– Be a user of topical ophthalmic medications of any pharmacological group.– Be a user of medicines by any other means of administration.– History of eye surgery in the last 6 months.– Wearing contact lenses for less than two weeks prior to the start of the study, and during the study intervention period.– For women: being pregnant, breastfeeding, or planning to become pregnant within the study period.– Have participated in any investigational clinical study 30 days prior to inclusion in this study.– Have previously participated in this same study.– History of any chronic-degenerative disease, including Diabetes Mellitus or Systemic Arterial Hypertension.– Known diagnosis of liver or heart disease.– Have active inflammatory or infectious disease at the time of study entry.

- Have unresolved injuries or trauma at the time of study entry.
- Having undergone surgical, non-ophthalmologic procedures within the past 3 months.
- Have received doses of vaccine against the Influenza virus or Coronavirus, 7 days prior to the inclusion of this study, or plan to receive it during the study intervention.
- Be or have an immediate family member (e.g., spouse, parent/legal guardian, sibling, or child) who is employed by the research site or sponsor, and who is directly involved in this study.
- Positive smoking (specified as cigarette smoking regardless of quantity and frequency, 4 weeks prior to study inclusion and during the study intervention period).
- Positive alcoholism (specified as the consumption of alcoholic beverages, regardless of quantity and frequency, 72 hours prior to the inclusion of the study and during the study intervention period).

Elimination criteria:

- Withdrawal of the informed consent form.
- Presentation of serious adverse event, whether or not related to the interventions, that, in the judgment of the Principal Investigator (PI) and/or sponsor, could affect the patient's ability to safely continue with study procedures.
- Non-tolerability or hypersensitivity to any of the compounds used during the tests (fluorescein, tetracaine).
- No tolerability or hypersensitivity to any of the investigational drugs.
- Adherence < 80% determined by the subject's diary and corroborated by the final weight of the research products (PI) with respect to the initial weight.

Duration of treatment: 7 days	Duration of the subject in the study: 13 days
Interventions:	

 • Investigational product, dosage, and route of administration: 
 - PRO- 231 . Moxifloxacin 0.5% Ophthalmic Solution. Laboratorios Sophia, S.A. de C.V. Zapopan, Jalisco, Mexico. - Dosage: 1 drop every 6 hours (3 daily applications [TID], in the right eye [OD]). - Route of administration: Topical ophthalmic. • Comparator product, dosage and route of administration: 
 - VIGAMOXI ® Moxifloxacino 0.5% Solución oftálmica. Alcon Laboratories, Inc., Fort Worth, Texas, USA. - Dosage: 1 drop every 6 hours (TID) in OD. - Route of administration: Topical ophthalmic. 	
Evaluation criteria:	

Primary outcome variables:***Safety***

- Incidence of Intervention-Related Unexpected AEs (Time to Assessment [ET]: Days 3, 8, and 12)
- Incidence of conjunctival hyperemia and chemosis. (TE: day 3 and 8)
- Changes in the AVMC evaluated with the Snellen chart. (TE: day 3 and 8)
- Changes in ocular surface integrity using fluorescein staining, using the Oxford scale. (TE: day 3 and 8).

Tolerability

- ICO score changes. (TEE: day 8)

Secondary outcome variables:***Safety:***

- Incidence of expected and intervention-related AEs (excluding conjunctival hyperemia and/or chemosis). (TE: day 3, 8 and 12)

[figure not shown]
Tolerability:

- Presence of eye symptoms (burning, foreign body sensation, pruritus and tearing). (TE: day 3 and 8)

Statistical methodology

The analysis of the data collected in the study will be carried out by means of specialized statistical software (SPSS available version or R software). The data will be expressed with measures of central tendency: mean, standard deviation and/or ranges for quantitative variables, and frequencies and/or percentages for qualitative variables. The Shapiro-Wilk test (S-W) will be used to determine if the distribution is normal in the data obtained in each study group ($p>0.05$). If the normality in the distribution of the data is verified, to rule out differences between groups, the Student's t-statistic will be used for independent groups, while intragroup differences will be analyzed with the Student's t-test for repeated measures. In case of $p<0.05$ in S-W, the statistical analysis to rule out differences between groups will be performed by means of the Mann-Whitney U test for quantitative variables, while intragroup differences will be performed by Wilcoxon's rank test. The difference between the qualitative variables will be analyzed by means of the χ^2 statistic (Chi-squared) or Fisher's exact (for expected values less than 5). Dichotomous variables will be analyzed by the McNemar test when applicable. An alpha (α) ≤ 0.05 will be considered as statistical significance, in addition to this, the 95% CI will be calculated for these differences. For primary outcome variables, H_0 will be rejected, when $p \leq 0.05$ and the 95% CI does not include zero.

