The frequency of adverse events with topical fluoroquinolone administration is low; The most frequent ocular adverse reactions reported after the application of the 0.5% moxifloxacin ophthalmic solution are: decreased visual acuity, dry eye, keratitis, eye discomfort, ocular hyperemia, eye pain, pruritus, subconjunctival hemorrhage, tearing and burning. The most frequent non-ocular adverse events reported are: dysgeusia, fever, cough, otitis media, pharyngitis, rash and rhinitis. . [1][13, 14]

The following adverse reactions have been reported during clinical studies with Moxifloxacin 5 mg/mL ophthalmic solution and are classified according to the following criteria: very common, occurring in 1 or more in 10 patients ($\geq 1/10$); common, occurring in 1 or more in 100 patients ($\geq 1/100$ to $< 1/10$); rare, occur in 1 or more in 1,000 patients ($\geq 1/1,000$ to $< 1/100$); rare, occurring in 1 or more in 10,000 patients ($\geq 1/10,000$ to $< 1/1,000$); very rare, there is less than one case in every 10,000 patients ($< 1/10,000$); or unknown frequency (a number cannot be estimated from the available data). Adverse reactions are ordered by organ or system affected, from the most severe to the mildest: [15, 16, 17]

Classification by organs and systems	Frequency	Adverse Reactions [MedDRA Preferred Terms (v.15.1)]
Blood and lymphatic system disorders	Strange	Decreased hemoglobin
Nervous system disorders	Rare	Headache
	Strange	Paresthesia (tingling or numbing sensation)
Eye disorders	Common	Eye pain, eye irritation

	Rare	Dry eye, conjunctival hemorrhage, red eye, itchy eyes, eyelid edema (swelling of the eyelids), eye discomfort.
	Strange	Corneal alteration, conjunctivitis, blepharitis (inflammation of the edge of the eyelids), conjunctival edema, blurred vision, decreased visual acuity, asthenopia (visual fatigue), redness of the eyelids.
Respiratory disorders	Strange	Nasal discomfort, pharyngolaryngeal pain (sore throat), foreign body sensation in the throat
Gastrointestinal disorders	Rare	Dysgeusia (bad taste in the mouth)
	Strange	Vomit

Additional adverse reactions identified in post-marketing surveillance include the following: frequency cannot be estimated from available data. Within each classification by organ and system, adverse reactions are presented from the most serious to the mildest. [15, 16, 17]

Classification by organs and systems	Adverse reactions [MedDRA preferred terms (v.15.1)]

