Immune system disorders	Hypersensitivity (allergic reactions)
Nervous system disorders	Seasickness
Eye disorders	Corneal ulcers, increased tearing, photophobia (sensitivity to light), eye discharge.
Heart disorders	Palpitations
Respiratory disorders	Dyspnea (shortness of breath)
Gastrointestinal disorders	Nausea
Skin disorders	Erythema (redness of the skin), purito (itching), rash (hives or blisters on the skin), hives (reddish hives that may cause itchy skin)

Available ophthalmic fluoroquinolones are indicated for the treatment of bacterial conjunctivitis and keratitis, with a treatment regimen of one drop three times daily for 7 days (the total duration of therapy will depend on the severity of the clinical picture and the course of the infection). In addition, they have been used off-label as prophylaxis in surgical procedures and ocular trauma to prevent endophthalmitis. However, because new molecules such as gatifloxacin and moxifloxacin have a higher spectrum and lower resistance, they should be reserved for the treatment of more severe eye infections.[8, 9, 15, 16] [17, 18] [17, 19]

There is no antimicrobial that provides ideal coverage for all pathogens at any site of infection. However, moxifloxacin 0.5% ophthalmic solution is a unique, preservative-free antibiotic (thanks to

its concentration it does not require the addition of preservatives to the formula), which offers broad-spectrum activity, and a moderate to high clinical success rate against common ocular pathogens. In addition to this, thanks to its concentration and its high penetrance to the ocular tissues, it allows a dosing regimen at infrequent intervals, simplifying its administration and making it more convenient for patients. [6, 7, 9, 10]

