7.4 Outcome variables

7.4.1 Primary outcome variables

7.4.1.1 Security

- Incidence of unexpected AEs related to interventions.
- Incidence of conjunctival hyperemia and chemosis.
- Changes in the AVMC evaluated with the Snellen chart.
- Changes in ocular surface integrity using fluorescein staining, using the Oxford scale.

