7.4.3 Definition of variables, methods and scales for their measurement

Board 2. Operational definition of variables

Variable	Conceptual Definition	Operational Definition	Measurement Type	Reference value	Statistical test
Incidence of Intervention-Related Unexpected AEs	Any adverse medical event that occurs in the clinical research subject to whom any of the interventions were administered and that has a certain coincidental relationship to the interventions [33]	All AEs (according to protocol) in which the PI suspects a causal relationship with the interventions will be reported	• Discrete quantitative • Nominal qualitative	• Relationship with IP • Severity • Causality	
 • Student's t-test of independent groups • U de Mann Whitney* • Pearson X² or Fisher Exact*
Incidence of conjunctival hyperemia	It is the reaction of the conjunctiva to a stimulus, a red appearance secondary to the vasodilation of the conjunctiva vessels of variable intensity is seen	Direct observation. Classification by Efron scale. See attachment 16.2. Efron Scale for Conjunctival Hyperemia	Degrees: 0 = Normal, I = Muy live, II = Mild, III = Moderate and IV = Severe		
 • Pearson X² or Fisher Exact* • McNemar Test*
Incidence of Chemosis	It is defined as conjunctival edema, the result of an inflammatory reaction. It is classified as present or absent	The evaluator will use a narrow beam of light at 60° and will measure whether the conjunctiva separates ≥ 1/3 of the total	• Nominal qualitative	Present / Absent	
 • Pearson X² or Fisher Exact* • McNemar Test*

Variable	Conceptual Definition	Operational Definition	Measurement Type	Reference value	Statistical test
Changes in the AVMC	Visual spatial acuity is the ability to distinguish separate elements of an object and identify them as a whole. It is quantified as the minimum angle of separation (located at the nodal point of the eye) between two objects that allows them to be perceived as separate objects	eyelid opening or if it exceeds the gray line Cartilla de Snellen. Ver anexo 16.5 Fraction to LogMAR conversion table.	• Continuous quantitative	20/30 (0.2 LogMAR) or better	
 • Student's t-test of independent groups • U de Mann Whitney*

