10.1.1 Calculation methodology

Although sample estimation in phase 1 studies is common in treatments whose toxicity/risk is high, as it is in clinical studies for the management/survival of cancer; It was considered pertinent to estimate the sample size according to the safety profile reported in the literature after the use of moxifloxacin hydrochloride. Considering the primary safety variables of the protocol: [59]

- Incidence of AD
- Changes in ophthalmologic signs
- Changes in the AVMC
- Changes in fluorescein staining of the ocular surface

The equation was used to compare two proportions: two samples, two sides of equality. This calculation is useful when you want to test whether the proportions of two groups are different (Incidence of AD in VIGAMOXI® is different from the incidence of AD in PRO-231). The following formulas are used for the calculation to compute the sample size and power respectively: [60]

$$n_A = kn_B \text{ y } n_B = \left(\frac{p_A(1 - p_A)}{k} \right) \left(\frac{z_{1-\alpha/2} + z_{1-\beta}}{p_A - p_B} \right)^2$$

$$1 - \beta = \Phi\left(z - z_{1-\alpha/2}\right) + \Phi\left(-z - z_{1-\alpha/2}\right), z = \frac{p_A - p_B}{\sqrt{\frac{p_A(1-p_A)}{n_A} + \frac{p_B(1-p_B)}{n_B}}}$$

Where:

$k = n_A/n_B$: ratio between the sample sizes of the two groups

Φ : Function of Standard Normal Distribution

Φ^{-1} : The standard normal quantile function

α : error tipo I

β : error tipo II

The proportion of subjects who had at least one AE (ocular and non-ocular) was considered in the study by Garg et al. (2015), where they evaluated the clinical and antibacterial efficacy, as well as the safety of besifloxacin ophthalmic suspension compared to moxifloxacin 0.5% (besifloxacin; n=61, moxifloxacin; n=62). A total of 6 ocular AEs were present in subjects treated with moxifloxacin and at least one AE occurred in 3 patients. The most common AE was conjunctivitis (3.2%). For the expected proportion of subjects of PRO-231, 50% was used, which is a conservative value and gives larger samples. The calculation was made using the free software R (R Core Team, 2021), using a code available online for this purpose. [56] [61] [62]

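### As named, the primary adverse-event variable counts only unexpected related events, so an excess of known moxifloxacin reactions that have no primary variable of their own does not feed the H0 decision; Table 2 and the sample size use a wider definition

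*Combined protocol and SAP*

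**What the plan says.** - **Name of the primary variable.** The Synopsis states the primary safety objective as "To compare the incidence of adverse events (AEs), unexpected, related to interventions", and section 7.4.1.1 gives the variable as "Incidence of unexpected AEs related to interventions". Section 3.1.2.1, the Table 2 row title and row C1 of Table 5 agree.
- **Expected events.** The Synopsis lists as secondary "Incidence of expected and intervention-related AEs (excluding conjunctival hyperemia and/or chemosis). (TE: day 3, 8 and 12"; sections 3.1.2.2 and 7.4.2.1 agree.
- **Decision rule.** To reject H0, "the p-value in the primary variables must be" at or below 0.05 and the 95% CI must exclude zero (Synopsis and section 3.2). The table in section 10.3.1 reads the opposite result as the two treatments being similar.
- **Operational definition.** For the variable titled as unexpected AEs, Table 2 says: "All AEs (according to protocol) in which the PI suspects a causal relationship with the interventions will be reported". It applies no expectedness filter.
- **Sizing.** Section 10.1.1 lists the primary variable simply as AE incidence and uses subjects with at least one AE. It adds: "For the expected proportion of subjects of PRO-231, 50% was used".
- **Known reactions.** The tables in section 2.1 include "Eye pain, eye irritation" as common and, from post-marketing data, "Corneal ulcers, increased tearing, photophobia (sensitivity to light), eye discharge" and hypersensitivity. Section 7.4.4.6 gives a different, shorter list for PRO-231.
- **Populations.** Primary variables are analysed per protocol (10.3.2.1), secondary variables in all dosed subjects (10.3.2.2).

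**The concern.** The trial asks whether a new moxifloxacin 0.5% formulation is as safe as a marketed one. With the active ingredient and strength the same, a plausible difference is a higher rate of reactions already known for the drug. A variable restricted to unexpected events leaves those out. PRO-231 could show more related AEs than the comparator while the AE primary shows few or none in either arm, and section 10.3.1 would count that towards similarity. The excess would appear only in a secondary variable that carries no weight in the decision.

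The restriction also does not match the plan's own operational definition or the quantity used for sizing. Two analysts could count different events for the same primary endpoint and both cite the protocol.

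**Working it through.** **1. Which reactions are affected.** The documents neither define unexpected nor name a reference list. Section 8.4 covers seriousness, severity and causality only. The two candidate lists compare as follows.

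| Reaction | 2.1 tables | 7.4.4.6 list | Other primary variable | Place under the named AE variable |
|---|---|---|---|---|
| Photophobia, dysgeusia | yes | yes | none | secondary only, on either list |
| Eyelid oedema, conjunctival haemorrhage, eye discharge, headache | yes | no | none | depends on the list |
| Hypersensitivity | yes | no | none | depends on the list |
| Corneal ulcer | yes | no | staining may register it | depends on the list |
| Whitish corneal precipitates | no | yes | none | depends on the list |
| Hyperemia, chemosis | yes | yes | own primary | reach the decision separately |

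Burning, foreign body sensation, pruritus and tearing are not AEs at all (7.4.4.3.4). They are secondary tolerability variables and touch the decision only as far as the comfort index at day 8 reflects them.

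**2. The plan's sample size.** The two-sided comparison of proportions with unpooled variance is

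n = [pA(1−pA) + pB(1−pB)] × [(z0.975 + z0.80) / (pA − pB)]²

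The plan states no power, so 80% is assumed, giving (1.960 + 0.842)² = 7.849.

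- pA = 6/62 = 0.0968, pB = 0.50: (0.0874 + 0.25) × 7.849 / 0.1626 = 16.29, so 17. This matches the plan, and 17 × 1.10 = 18.7 gives 19 per arm.
- pA = 3/62 = 0.0484, pB = 0.50: (0.0460 + 0.25) × 7.849 / 0.2040 = 11.39, so 12.

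The match needs 6/62, although section 10.1.1 reports 6 ocular events and 3 patients with an AE. That is a separate matter, so both rates are carried below. On either rate, the sizing input is AEs without an expectedness filter.

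**3. Power if all related AEs count.** This is exact enumeration of two binomials under the planned rule: Fisher if any expected count is below 5, otherwise Pearson without continuity correction, two-sided 0.05. The sizing rates are for any AE and are read here as related-AE rates, which is an assumption.

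| PRO-231 vs comparator | 17 per arm | 19 per arm |
|---|---|---|
| 50% vs 3/62 | 86% | 91% |
| 50% vs 6/62 | 73% | 81% |
| 25% vs 3/62 | 23% | 29% |
| 15% vs 3/62 | 5% | 6% |
| 10% vs 3/62 | 1% | 1% |

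**4. Power if only unexpected related AEs count.** The share of affected subjects with an unexpected event is not in the documents. As illustrations, at 19 per arm:

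- Share 10%: 5% vs 0.48%, power 0.2% (with 6/62: 5% vs 0.97%, 0.2%).
- Share 20%: 10% vs 0.97%, power 3% (with 6/62: 10% vs 1.94%, 2.5%).
- Share zero: 0/19 vs 0/19, so no rejection is possible.

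With 0/19 in one arm, Fisher gives p = 0.105 for 4/19 in the other and p = 0.046 for 5/19. Five subjects with unexpected related events are therefore needed against none.

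**The case against.** The strongest reply is that Table 2 already counts every AE with suspected causality, so nothing is excluded. This defeats a reading that some may draw, namely that known reactions cannot enter the AE part of the decision. The documents do not settle that. But Table 2 does not cure the problem either. Its row for expected AEs has nearly the same operational wording, so read literally the two rows coincide and only their names separate them. The restriction to unexpected events is repeated in the objectives, the outcome list and Table 5.

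A reader might also infer that corneal ulcer and hypersensitivity are shut out. That holds only if the section 2.1 tables define expected. On the section 7.4.4.6 list both would be unexpected and would count, and corneal epithelial defects are in any case what the staining variable looks for.

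Other primaries do catch part of an excess: hyperemia, chemosis, visual acuity, staining and the comfort index, which includes an item on pain. Expected related AEs are still compared between arms, with the same tests, as a secondary variable. All of this stands and lowers the weight of the point.

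A contrast of 91% against zero would overstate the gain from a wider definition. The 91% rests on a 50% rate chosen as conservative for sizing, and the zero assumes that no event is unexpected. At modest excesses the sample size limits detection under either definition.

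Finally, simply moving expected AEs into the primary tier would move them from all dosed subjects to the per-protocol set. Intolerance or hypersensitivity to study drug is an elimination criterion (5.2.1), so that set can lose the subjects who reacted. This objection is sound, and the fix has to meet it.

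**Conclusion.** The point holds in limited form. As named, the primary AE variable leaves an excess of expected related AEs without their own primary variable outside the H0 rule. Photophobia and dysgeusia are examples whichever list applies. The name conflicts with Table 2's operational definition and with the any-AE quantity used for sizing. Whether corneal ulcer, hypersensitivity and several other reactions are affected is undetermined until the plan names its reference for expected.

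The size is conditional. Counting all related AEs gives 91% power at 19 per arm (86% at 17) under 50% versus 3/62, 81% at 19 with 6/62, and about 29% at 25% versus 4.8%. The 0.2% and 3% figures for the restricted variable rest on illustrative unexpected shares of 10% and 20%. This should be corrected, but it does not mean that the trial is blind to known reactions.

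**What to change.** - In the Synopsis, sections 3.1.2.1 and 7.4.1.1, Table 2 and Table 5, define the primary AE variable as the proportion of subjects with at least one intervention-related AE, expected or unexpected.
- In section 10.3.2.1, analyse this variable in all subjects who received at least one dose (the safety population of 10.3.2.2), not in the per-protocol set.
- Keep hyperemia and chemosis as separate primary variables, and state whether they also count in the AE variable.
- Name one reference list for expectedness, reconcile sections 2.1 and 7.4.4.6 with it, and report the expected/unexpected split with a listing of every unexpected event.

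The cost is an amendment to the wording and to the analysis set for one primary variable. Visits, data collection and the test are unchanged. The small downside is that the headline AE figure no longer isolates new risks; the split and the listing still show them.
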